Name	Created	Modified Date
 COVID_questionnaire_05 18 2020.docx(0.01)	5/18/2020 3:28 PM	5/18/2020 3:28 PM
 PAM PH(0.01)	9/25/2019 5:13 PM	9/25/2019 5:13 PM
 Health and Wellness Utilization.docx(0.01)	9/3/2019 1:21 PM	9/3/2019 1:21 PM
 Mental Health Confidence Scale.docx(0.01)	9/3/2019 1:21 PM	9/3/2019 1:21 PM
 Omnis Salutis Utilization.docx(0.01)	9/3/2019 1:21 PM	9/3/2019 1:21 PM
 Technology Use.docx(0.01)	9/3/2019 1:21 PM	9/3/2019 1:21 PM
 WHODAS2.0_36itemsSELF.pdf(0.01)	9/3/2019 1:21 PM	9/3/2019 1:21 PM
 AUDIT-C(0.02)	10/20/2016 3:55 PM	7/5/2019 1:44 PM
 Patient Participation subscale of the Patient Empowerment Scale.docx(0.01)	2/26/2019 2:09 PM	2/26/2019 2:09 PM
 Demographic Form Provider(0.01)	6/26/2017 2:26 PM	6/26/2017 2:26 PM
 Demographic Form Veteran(0.02)	10/20/2016 3:50 PM	6/26/2017 2:26 PM
 Client Satisfaction Questionnaire.docx(0.01)	10/20/2016 3:57 PM	10/20/2016 3:57 PM
 PAM MH.pdf(0.01)	10/20/2016 3:56 PM	10/20/2016 3:56 PM
 DAST-10 substance abuse measure.pdf(0.01)	10/20/2016 3:55 PM	10/20/2016 3:55 PM
 PCL-5.pdf(0.01)	10/20/2016 3:55 PM	10/20/2016 3:55 PM
 dass21.doc(0.01)	10/20/2016 3:54 PM	10/20/2016 3:54 PM
 VR-36 FORM Version 1.0.doc(0.01)	10/20/2016 3:52 PM	10/20/2016 3:52 PM
 MIRECC VA PCC WAI-C (42250 - Activated, Traditional).pdf(0.01)	10/20/2016 3:51 PM	10/20/2016 3:51 PM

Name	Created	Modified Date
 MIRECC VA PCC PICS (52028 - Activated, Traditional).pdf(0.01)	10/20/2016 3:51 PM	10/20/2016 3:51 PM
 Consultation Care Measure.docx(0.01)	10/20/2016 3:51 PM	10/20/2016 3:51 PM

3 * **What is the total length of time that each survey is expected to take?**

Aim 1 surveys: 15 minutes

Aim 2 surveys (acceptability trial participants): 40 minutes per time point

Aim 3 surveys: up to 60 minutes per time point

4 * **Are any of the questions likely to cause discomfort in participants or cause harm if their confidentiality were breached? (i.e., Illegal activities)**

Yes No

5 * **Do any questions elicit information related to the potential for harm to self or others?**

Yes No

5.1 **If Yes, what procedures are in place to assure safety?**

ID: VIEW4E09460F5EC00
Name: v2_Surveys/Questionnaires

Interviews

You indicated that this study involves key informant or semi-structured individual interviews.

1 * Are any of the questions likely to cause discomfort in participants or cause harm if their confidentiality were breached? (i.e., Illegal activities)

Yes No

2 * Upload a copy of the interview script or guide that will be used to guide the interviews:

Name	Created	Modified Date
 PCC Aim 3 Qual interview guide.docx(0.02)	5/1/2020 3:19 PM	5/1/2020 3:39 PM
 Acceptability Individual Interview Script.docx(0.01)	10/20/2016 4:11 PM	10/20/2016 4:11 PM

3 * What is the individual duration of each interview and what is the entire duration of the interviews?

One hour

4 * How will the interview responses be recorded and by whom?

The interviews will be audio recorded by a member of the research staff and transcribed by a professional transcriptionist.

5 * Do any questions elicit information related to the potential for harm to self or others?

Yes No

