Specific Aim 3: Conduct a pilot randomized controlled trial of the brief, Veteran-targeted PCI in a sample of recent Veterans with stress-related mental health disorders (n=48) to assess feasibility and preliminary efficacy.

Hypothesis 3a: The brief PCI will be shown to be feasible as evidenced by successful rates of recruitment, attendance at intervention sessions by Veterans, and interventionist fidelity to the intervention.

Hypothesis 3b: Compared to a health and wellness control intervention, participation in the brief, Veteran targeted PCI will result in significant increases in (1) Veteran PCC behaviors in mental health care encounters and (2) functioning in domains of health, purpose, and community.

Secondary analysis: Comparing the RCT arms, explore (1) Veteran attrition from VA mental health care via chart review and (2) Veteran self-assessment of levels of clinical symptomology with the DASS-21, AUDIT, DAST 10, and PCL-5.

2 * Discuss the research design including but not limited to such issues as: probability of group assignment, potential for subject to be randomized to placebo group, use of control subjects, etc.:

Aim 1: 35 recent Veterans with stress-related mental health disorders and their VA mental health providers will consent to audio-recording of one treatment encounter. (There is no randomization or group assignment.)

Aim 2: Two focus groups of 4-6 Veterans each will be held. We will also conduct a clinical demonstration of the PCI with 10 Veterans to examine acceptability and further refine the intervention. Participants will complete the three session intervention and participate in a qualitative interview about their experience. (There is no randomization or group assignment.)

Aim 3: We will conduct a pilot randomized controlled trial of the PCI (n=48) to assess feasibility and preliminary efficacy. 24 participants will be randomized to a health and wellness control condition and 24 to the experimental treatment condition.

3 * Describe the relevant prior experience and gaps in current knowledge. Describe any relevant preliminary data:

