Following the recorded Veteran/provider encounter, participants will have the option of completing the surveys in person or taking the surveys and a pre-addressed, stamped envelope and returning the surveys at a later time. If participants have not returned the surveys within one week a study team member will follow-up by phone and offer to conduct the surveys by phone. Participants will be mailed their participation compensation funds upon receipt of the survey data.

Aim 2: Intervention development will be led by a multi-stakeholder Expert Advisory Panel and further developed using Veteran focus groups. Acceptability will be demonstrated via qualitative interviews following a pre-pilot demonstration project with 10 Veteran participants. Ten Veteran participants will receive the intervention. There will be no randomization or control condition. Veterans will complete survey measures after consenting to participate in the trial. Following participation in the intervention the Veteran participants will complete survey measures and a qualitative interview face-to-face.

Following conclusion of Aim 2, the Expert Advisory Panel (EAP) will discuss the results of Aim 1 and Aim 2 as a group and determine if any changes need to be made to enhance utility or improve intervention delivery prior to Aim 3. To determine readiness to proceed to Aim 3, the EAP will hold an anonymous vote during EAP Meeting 4. At least 75% of present EAP members must approve the intervention to move into randomized controlled trial (RCT) testing before Aim 3 will commence. If the EAP does not vote to proceed, the research team will make recommended modifications, present the updated intervention at a new meeting, and the EAP will vote again to proceed. If necessary this process will continue until the EAP approves the intervention for testing in the pilot RCT. A modification reflecting the final intervention will be submitted once the intervention has been finalized.

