We will use VA email to communicate with potential veteran participants and veteran participants during the acceptability trial and the RCT in order to recruit participants and send electronic copies of resources, blank worksheets, and/or response cards for them to use at a later time. When sending any documents for the initial consent appointment we will use a VA-approved method in order to encrypt the email message and add this extra security measure. We will only send follow up emails and/or these materials at the veteran's request and staff will discuss proper procedures for communication via email with the veterans ahead of time to ensure understanding. The emails will also include a clear statement that no completed forms or personal identifying information should be sent to staff via email correspondence. For instance,

Signature for sign-off

Email is not secure. Please do not reply back to this message with any personal information or personal health information.

If you are having thoughts of harming yourself, please call the Veterans Crisis Line at [name].

* Confidentiality Notice *

This electronic message may contain confidential and legally protected information, intended only for the use of the individual or entity named in the message header. If you are not the intended recipient, you are hereby notified that any disclosure, copying, distribution, or action taken in reliance on the contents of this electronic message and/or any attachments is strictly prohibited. If you have received this electronic message in error, please notify the sender immediately to arrange for your electronic email address to be removed from the sender's personal address book and/or distribution list.

Potential participants

1. Email script for potential participants

Subject: research study eligibility

Hello,

I am on a research team that studies mental illness at the VA Maryland Health Care System. Currently, we are conducting a research study about ways to improve VA mental health care.

We would like to let you know that we believe you may be eligible for one of our studies. Your participation is entirely voluntary. If you do not want to participate, you will receive the same quality of care currently available to you. If you agree to participate, you will be reimbursed for your time and effort.

If you would like more information about this study, please respond to this email with YES OR call [staff] at XXX-XXX-XXXX.

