If you do not want us to contact you, please respond to this email with NO.

If you do not respond we will contact you by phone to follow-up on this letter.

We cannot guarantee email is secure so please do not reply back to this message with any personal information or personal health information.

Thank you and have a great day!

2. Email script for potential participants who ask for more information via email

Subject: research study eligibility

Hello,

Per your request, here is information on the VA research study you are eligible for.

The study involves several types of appointments which take 6 hours of time split over multiple remote visits. We are currently conducting all visits over the phone and through encrypted, secure video chatting. To complete these appointments, you will need a computer/tablet with a microphone and camera or a smart phone. In the first appointment we would complete the informed consent paperwork for this study and have you complete a few questionnaires (1-1.5 hours). You would then be matched with a study interventionist who will call you to schedule your individual meetings. You would meet three times for individual educational meetings where you will learn about patient-centered health care. These meetings can be scheduled during times that are convenient for you and would take about 1 hour per session. All visits with study interventionists will be conducted through encrypted, secure, telehealth video conferencing. Approximately three and six months after the individual sessions are done you will complete study questionnaires. These would take about 45 minutes each. Each of the four times you complete questionnaires you will be compensated \$50 for a total of \$200 for your time. This payment will arrive in the form of an emailed gift card to Safeway or a check in the mail.

If you are interested in hearing more specifics, please respond with a good time to call you or call [VA staff] at XXX-XXX-XXXX. If you are no longer interested, please respond to this email with NO.

We cannot guarantee email is secure so please do not reply back to this message with any personal information or personal health information.
Thank you and have a great day!

3. Email script for potential participants who have expressed interest in study participation

Subject: research study eligibility

Hello,

As you requested, we're following up about your interest in participating in a VA research study.

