- If meeting face-to-face with a veteran for their individual session(s) is not possible then a trained study interventionist may (1) transport a study audio recorder to capture the audio of any individual session(s) completed via telehealth visit or (2) utilize the VA's protocol for Recording in CAG using Audacity Application and will export the recording to a restricted access VA sharedrive. If the interventionist uses an audio recorder they will utilize their locked HIPAA bag to transport the recorder, to ensure its protection.

- If meeting face-to-face with a veteran for their regularly scheduled mental health care is not possible and the veteran has provided consent to record one of their regularly scheduled mental health care appointments, then the study team will approach the veteran's mental health care provider to ask if they are willing to utilize the VA's protocol for Recording in CAG using Audacity Application. If they agree then the study team will make arrangements with the clinician to receive the recording via a sharedrive and immediately export the recording to a restricted access VA sharedrive.

Behavioral Intervention

You indicated that this study involves psychosocial or behavioral interventions.

1 * Describe the intervention (duration, number of sessions, focus, etc.):

Aim 3

Treatment condition. We anticipate that the person-centered intervention (PCI) will be comprised of three, one-hour sessions offered over three to six weeks, scheduled at the participants' preference. Sessions will be one-on-one with the interventionist. The PCI sessions will be offered in a private room in the same buildings that VA mental health services are located in, on the two respective VAMHCS campuses OR will be offered via VA Video Connect, the VA's telehealth program which uses encryption to ensure a secure and private session, OR phone.

Control condition. The control condition will be an educational health and wellness intervention for stress related disorders that will match the experimental condition for time and attention. The control condition will be three, one hour, individual sessions covering the symptom cycle, managing stress, and identifying social supports. The interventionist will be a non-blinded member of the research team such as the

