2 * What is the total dollar value of the payments/reimbursements over the duration of the study? **Total payment(s) for participation in research of \$600 or more in a calendar year is required to be reported on an IRS Form 1099.**

\$50/\$25/\$60/\$125/up to \$200/up to \$250

3 * Describe the timing and distribution plan for the payment/reimbursement (schedule, means, etc.)?

Because participants can only participate in one Aim/subsection of the study over the course of the whole study, the most one participant could receive is \$125. Here is the timing and distribution of each aim/subsection.

Aim 1: one time payment of \$50 following the research interview

Aim 2a: one time payment of \$25 following focus group participation.

Aim 2b: payment of \$20 following baseline research interview and \$40 following post research interview and qualitative interview participation.

Aim 2c: Five payments of \$25 each following each Expert Advisory Panel meeting.

Aim 3: Four payments of \$50 each following each research interview (up to \$200) and the potential for additional \$50 if selected for qualitative interview participation (\$250 total if selected for additional qualitative interview). Please note: for RCT participants who have completed some of their assessments prior to this study modification (anyone already enrolled) they will receive the increased amount of \$50 for any remaining, future assessments they complete as part of the study

Participants will be paid upon receipt of completed data. Research staff will initiate payment via the agent cashier (if using VA voucher) or via electronic gift card depending on which method is preferred by the participant. If a participant selects the gift card option, research staff will send their electronic gift card via email using approved email script.

4 * Method(s) of payment/reimbursement to be Used:

- Cash
- Check
- Money Order
- Gift Certificate/Gift Card
- Other

4.1 If Other, specify:

Veteran participants will either be given a gift card, check, VA voucher, or an equivalent payment method.

HIPAA (Health Insurance Portability and Accountability Act)

1 * Are you affiliated with, or will you be accessing data from a HIPAA-covered entity? A covered entity might be a hospital, a physician practice, or any other provider who transmits health information in electronic form.

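### Email script 2 tells RCT candidates who ask for details that their sessions teach patient-centered care, which is untrue for those later allocated to the control arm

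*Combined protocol and SAP*

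**What the plan says.** The protocol prints the same email scripts twice, under Study Procedures, item 1, and under Recruitment, item 1. They are meant for "potential veteran participants and veteran participants during the acceptability trial and the RCT in order to recruit participants". The script at issue is headed "2. Email script for potential participants who ask for more information via email". On the content of the sessions it says: "You would meet three times for individual educational meetings where you will learn about patient-centered health care". It then moves from consent and baseline questionnaires to pairing with an interventionist. It mentions neither randomization nor a second program.

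The design statement for Aim 3 (Justification, Objective, & Research Design, item 2) reads: "24 participants will be randomized to a health and wellness control condition and 24 to the experimental treatment condition". Under Behavioral Intervention, item 1, the control is described as follows: "The control condition will be three, one hour, individual sessions covering the symptom cycle, managing stress, and identifying social supports". Education about patient-centered care is the content of the experimental intervention, according to the scientific background in item 4 of the Justification section.

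**The concern.** The script reaches a candidate before consent and describes what that person's own sessions will teach. In a two-arm trial it describes one arm as if it were the whole study. A Veteran who enrolls on that understanding and is then taught about the symptom cycle, stress and social supports has not received what the email described, and may work out which arm they are in.

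Four features of the plan could make this matter:

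- Functioning (VR-36, WHODAS) and symptoms are self-reported, so disappointment in the control arm could lower ratings or increase dropout.
- Veteran behavior in the recorded visit (MPCC) is assessed only at time point 2, so there is no baseline MPCC score to adjust for.
- That recording is optional, and the Veteran decides about it after the sessions are over. Willingness to be recorded could therefore differ by arm.
- Recruitment feasibility is measured as consents over approaches. A consent rate obtained partly with a message describing only the active arm is a less clean guide for a larger trial.

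**Working it through.** No effect estimate can be computed here. The check is whether the script belongs to the RCT, and whether its sentence is true for both arms. The plan's power figure (d = .65) plays no part.

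**Step 1. Which study does the script describe?**

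| Feature | Script 2 | Aim 3 RCT | Aim 2 acceptability trial |
|---|---|---|---|
| Questionnaire payments | 4 × $50 = $200 | 4 × $50 = $200 | $20 + $40 = $60 |
| Follow-up | about 3 and 6 months after the sessions | 3 and 6 months | one assessment after the intervention |
| Sessions | 3, about 1 hour each | 3, 1 hour each | 3 |
| Stated total time | 6 hours | about 8 hours | up to 6 hours |

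The payment rows rest on "Each of the four times you complete questionnaires you will be compensated" in the script and "Aim 3: Four payments of" in Payment/Reimbursement Detail, item 3. Both are followed by $50.

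The total time is the one row that fits Aim 2 better. The script's own components are 1 to 1.5 hours for the first appointment, 3 × 1 hour of sessions and 2 × 0.75 hour of follow-up:

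- 1 + 3 + 1.5 = 5.5 hours
- 1.5 + 3 + 1.5 = 6.0 hours

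That sum includes three questionnaire occasions, although the script pays for four. The 6 hours therefore leaves out one RCT assessment and is not evidence of an Aim 2 script. The payments and the three- and six-month follow-up settle the matter in favor of Aim 3.

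**Step 2. Is the sentence true for everyone in that study?**

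- Aim 2 acceptability trial: "Ten Veteran participants will receive the intervention. There will be no randomization or control condition". With a single arm receiving the intervention, the sentence would be true for all ten.
- Aim 3, experimental arm: the sessions teach patient-centered care, so it is true.
- Aim 3, control arm: the three listed topics do not include patient-centered care, so it is untrue.

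**Step 3. How far does it reach?**

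The control share is 24/48 = 50%. If *m* randomized Veterans had received the script, and allocation is 1:1 and unrelated to receiving it, the statement would be untrue for *m*/2 of them on average. The documents do not give *m*.

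**Step 4. Can the direction of bias be signed?**

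- Disappointed controls who rate themselves lower would move the comparison toward the intervention.
- Controls primed to take a more active part in their visits would move it away from the intervention.
- Arm-related dropout or refusal of the recording could act either way.

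The documents give nothing with which to weigh these against each other, so neither the size nor the net sign can be derived.

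**The case against.** The strongest reply is that this is one sentence in a secondary script, and that its effect on the trial is conjecture. Several parts of that reply stand.

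- **Reach.** A reader might infer that every candidate is told this, or that all 24 controls receive it. The documents do not support either reading. By its heading, script 2 goes only to people who ask for details by email. The first-contact email speaks only in general terms of improving VA mental health care. Candidates also arrive by letter, clinician referral, flyer, newsletter and in-person approach. The script describes all visits as currently remote, whereas the consent section refers to Aim 3 participants enrolled before March 2020, when in-person visits stopped.
- **Consent.** Before enrollment, staff review the consent form in detail, and the Veteran must pass a set of questions about the study. That review may explain both arms and correct the impression. The consent forms are not in the public documents, so this cannot be checked either way.
- **Concealment.** A reader might infer that the email breaks participant blinding. The documents state no such blinding. They match the control for time and attention, which is a different aim. Flyer and newsletter text under Advertising Detail already names person-centered mental health care as the subject of the research, and several RCT questionnaires point to it as well.
- **Size.** A reader might want to express the harm as a fraction of the d = .65 in the power statement. That figure is the effect detectable with 80% power. Any expectancy shift set against it would be an assumption without support in the documents.

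None of this makes the sentence true for the control arm. The flyers name the topic of the study, whereas script 2 tells recipients what their own sessions will teach. If the consent form does describe two arms, the email conflicts with it; if it does not, the email goes uncorrected. Either way the sentence needs changing.

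**Conclusion.** The point holds as an inaccuracy in participant-facing text. Script 2 describes the experimental content to RCT candidates without condition and omits random allocation, so it is untrue for recipients later allocated to the health and wellness control. This rests on assigning the script to Aim 3, which the payment schedule and follow-up times support despite the 6-hour total.

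Its reach is unknown, because the number of Veterans who ask for details by email is not given. Its effect on the self-reported and MPCC outcomes is possible but cannot be quantified or signed. It is not a demonstrated design flaw or a breach of blinding. It is an avoidable source of arm-specific expectations in a trial whose outcomes could respond to them.

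**What to change.** In both copies of script 2 (Study Procedures, item 1, and Recruitment, item 1), replace the sentence with wording true for both arms. For example: the Veteran would have three individual educational meetings in one of two health-related programs, and the program would be decided by chance. Make the same change in the uploaded email-script file, and check that it agrees with the Aim 3 Veteran consent form.

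The change makes the description accurate and limits arm-specific expectations. It does not conceal the study topic, which the flyer and newsletter text will still name. The cost is one IRB modification and a slightly less specific message to candidates. Design, sample size and analysis are unaffected.
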